### 6.2.1 Inclusion criteria

Patients will be included in this study if they meet all of the following inclusion criteria:

1. Patient (adult or pediatric) is $\geq 2$ years of age *
2. Patient has a physician confirmed/documented diagnosis of PROS*
3. Patient has a documented evidence of a mutation in the PIK3CA gene*
4. Patient's condition was assessed by the treating physician as severe or life threatening and treatment was deemed necessary*
5. Patient has been treated with at least one dose of alpelisib, initiated on or before 23-Sep-2019 (i.e. at least 24 weeks before the cut-off date of the 09-Mar-2020)
6. Patient has medical chart history available during enrollment in the MAP
7. Patient (in case of pediatric patients assent and/or parent/guardian consent) consented to participate in the study (as required by local ethics regulations)
* Inclusion criteria for MAP enrollment (assessed at the time of alpelisib initiation).

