Concomitant medications (other than alpelisib) include medications starting on or after the index date or medications starting prior to the index date and continuing after index date. Concomitant medications will be coded using the World Health Organization (WHO) Drug Reference Listing (DRL) dictionary that employs the WHO Anatomical Therapeutic Chemical (ATC) classification system and summarized by lowest ATC class and preferred term using frequency counts and percentages.

Duration of alpelisib exposure, cumulative dose, dose intensity (DI) and relative dose intensity (RDI) will be summarized by age. The number of patients with dose reductions/interruptions, and the reasons, will be summarized and listed.

Duration of exposure to alpelisib defined as follow:

Duration of exposure (days) = (last date of know exposure to alpelisib) – (index date) + 1.

The last date of exposure is the last date when a nonzero dose of study drug is administered and recorded in the (e)CRF. For patients who are still receiving treatment at the time of cut-off date, the cut-off date will be used as last exposure date. The duration of exposure includes the periods of temporary interruption.

Summary of duration of exposure of alpelisib will include categorical and continuous summaries (i.e. mean, standard deviation etc.) using appropriate units of time (months).

Cumulative dose is defined as the total dose of the alpelisib given during the study. Cumulative dose will be summarized using descriptive statistics.

Dose intensity (DI) is defined as: $DI \text{ (mg/day)} = \text{Cumulative dose (mg)} / \text{Duration of exposure (days)}$.

Planned dose intensity (PDI) is the assigned dose by unit of time planned to be given to patients; at the start of treatment; generically 250 mg for adults and dose of 50 mg for pediatric patients are used per day.

Relative dose intensity (RDI) is defined as: $RDI \text{ (\%)} = DI \text{ (mg/day)} / PDI \text{ (mg/day)} * 100$

The number (%) of patients with dose reductions or interruptions and permanent discontinuations, and associated reasons, will be summarized.

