4.1 General definitions

Study treatment

The term study treatment or study drug will be used in this document and will refer to alpelisib.

Date of first administration of study drug

The date of first administration of alpelisib is defined as the first date when a non-zero dose of alpelisib is administered and recorded in the (e)CRF. This date is referred to as index date and used as reference start date.

Date of last administration of study drug

The date of last administration of alpelisib is defined as is the last date when a nonzero dose of alpelisib is administered and recorded in the (e)CRF.

Study day

The study day, describes the day of the event or assessment date, relative to the reference start date. The study day is defined as:

- The date of the event (visit date, onset date of an event, assessment date etc.) – reference start date + 1 if event is on or after the reference start date;
- The date of the event (visit date, onset date of an event, assessment date etc.) – reference start date if event precedes the reference start date.

Time unit

A year length is defined as 365.25 days. A month length is 30.4375 days (365.25/12). If duration is reported in months, duration in days will be divided by 30.4375. If duration is reported in years, duration in days will be divided by 365.25.

Baseline

For safety and efficacy evaluations, the last available assessment on or before the date of start of alpelisib is defined as “baseline” assessment.

On-treatment assessment/event and observation periods

For adverse event reporting the overall observation period will be divided into two mutually exclusive segments:

1. *pre-index date/pre-treatment period*: from up to 24 weeks prior to the index date through to the day prior to the index date.
2. *post-index date/on-treatment period*: from date of first administration of study treatment to 30 days after date of last administration of alpelisib (including start and stop date).

Safety summaries (tables, figures) include only data from the on-treatment period with the exception of baseline data which will also be summarized where appropriate (e.g. change from baseline summaries).

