4.3 Imputation rules

4.3.1 AE, ConMeds and safety assessment date imputation

Table 4-1 Imputation of start dates (AE, Symptoms and complications, concomitant medications medical history, health resources utilization, non-drug treatment and other medical interventions)

Missing Element	Rule
day, month, and year	
 • No imputation will be done for completely missing dates
day, month	
 • If available year = year of study treatment start date (index date) then 
 ○ If stop date contains a full date and stop date is earlier than study treatment start date then set start date = 01JanYYYY ○ Else set start date = study treatment start date. • If available year > year of study treatment start date then 01JanYYYY • If available year < year of study treatment start date then 01JulYYYY
Day	
 • If available month and year = month and year of study treatment start date then 
 ○ If stop date contains a full date and stop date is earlier than study treatment start date then set start date= 01MONYYYYY. ○ Else set start date = study treatment start date. • If available month and year > month and year of study treatment start date then 01MONYYYYY • If available month and year < month year of study treatment start date then 15MONYYYYY

Table 4-2 Imputation of end dates (AE, Symptoms and complications, concomitant medications, medical history, health resources utilization, non-drug treatment and other medical interventions)

Missing Element	Rule (*= earliest between (last treatment date plus 30 days, death date, cut-off date)
day, month, and year	
 Completely missing end dates (incl. ongoing events) will be imputed by the end date of the study period*
day, month	
 If partial end date contains year only, set end date = earliest of 31DecYYYY or end date of the study period*
Day	
 If partial end date contains month and year, set end date = earliest of last day of the month or end date of the study period*

Table 4-3 Imputation of start dates for assessments (Laboratory evaluation, vital signs, ECG, growth data, medical procedure (surgery), death, questionnaires, PROS disease history)

Missing Element	Rule
day, month, and year	
 No imputation will be done for completely missing dates

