day, month	
 If available year = year of study treatment start date (index date) then set start date = max(study treatment start date, 01JulYYYY). If available year > year of study treatment start date then 01JanYYYY If available year < year of study treatment start date then max (01JulYYYY , Pre-Index date)
Day	
 o If available month and year = month and year of study treatment start date then set start date = max(study treatment start date, 15MONYYYY). • If available month and year > month and year of study treatment start date then 01MONYYYY • If available month and year < month year of study treatment start date then max(15MONYYYY , Pre-index date)

If imputed date is before birth or after DCO, death date or study discontinuation the last will be used.

If imputed end date is earlier than the start date or of the imputed start date then the imputed end date = start date.

Any AEs and ConMeds with partial/missing dates will be displayed as such in the data listings.

Any AEs and ConMeds which are continuing as per data cut-off will be shown as 'ongoing' rather than the end date provided.

For treatment start and end date if day is missing then it will be set to be the 15th of the month and if both month and day are missing, is defaulted to 01-Jan.

Treatment end date = min (imputed treatment end date*, death date, cut-off date).

If Imputed treatment end date < Treatment start date then Treatment end date= treatment start date.

Similar imputation will be performed for similar assessment in the pre-index period, more details as will be provided in the PDS.

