4.3.1.2 Other imputations

Partial dates

For imputation of the partial dates when not otherwise specified the following rule will apply: missing day is defaulted to the 15th of the month and missing month and day is defaulted to 01-Jan.

Incomplete lesion assessment dates

All investigation dates (e.g. MRI scan, CT scan) must be completed with day, month and year. If one or more assessment dates are incomplete but other investigation dates are available, this/these incomplete date(s) are not considered for calculation of the assessment date and assessment date is calculated as the earliest date of all investigation dates at that evaluation number. If all measurement dates have no day recorded, the 1st of the month is used. If the

month is not completed, for any of the investigations, the respective assessment will be considered to be at the date which is exactly between previous and following assessment. If a previous and following assessment is not available, this assessment will not be used for any calculation.

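### The 01-Jan default for an alpelisib date known only by year can give a 1-day exposure and move the Week 24 window by months, and the 15th default can flip the 24-week discontinuation criterion near its threshold

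*SAP*

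**What the plan says.** After Table 4-3, SAP 4.3.1 gives one rule for alpelisib start and end dates: with the day missing, "it will be set to be the 15th of the month and if both month and day are missing, is defaulted to 01-Jan". The end date is then capped: "Treatment end date = min (imputed treatment end date*, death date, cut-off date"). If the result precedes the start, "If Imputed treatment end date < Treatment start date then Treatment end date= treatment start date". SAP 4.3.1.2 repeats the same default for partial dates not covered elsewhere: "missing day is defaulted to the 15th of the month and missing month and day is defaulted to 01-Jan".

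For other partial end dates, such as those of adverse events and concomitant medications, Table 4-2 goes the other way: "If partial end date contains year only, set end date = earliest of 31DecYYYY or end date of the study period".

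The first-dose date carries much of the analysis. SAP 4.1 says of it: "This date is referred to as index date and used as reference start date". It anchors the baseline scan window (SAP 3.2: index date or up to 24 weeks before) and the Week 24 window (SAP Table 3-1: from 20 to under 32 weeks). With the stop date it fixes exposure, computed as stop minus index plus 1 (SAP 3.6), and the on-treatment period, which ends 30 days after the last dose or at cut-off if sooner (SAP 3.6, endpoint #10). Stopping alpelisib for good before 24 weeks makes a patient a non-responder (SAP 3.5.1).

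**The concern.** A year-only date is placed at the first day of the year for start and stop alike. For a stop, that is the shortest exposure the record allows. For a start, it is the earliest possible index date, so every scan appears later in treatment than it was. Both dates feed the primary endpoint. The readable text does not exempt imputed treatment dates from the response derivation, bound them from below by known doses or visits, or test them: the sensitivity analyses in SAP 3.5.3 deal only with missing response. At stake are response status, membership of the efficacy population, and the on-treatment adverse event tables.

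**Working it through.** **Inputs.** Last permitted start 23-Sep-2019 and cut-off 09-Mar-2020 (Protocol 6.2.1); imputation rules (SAP 4.3.1); Week 24 window of 20 to under 32 weeks and baseline window of 24 weeks (SAP 3.2, 3.3); exposure formula (SAP 3.6); 24-week criterion (SAP 3.5.1), taken as 24 × 7 = 168 days; 50 patients (Protocol 6.6).

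**The plan's own date figure.** 09-Mar-2020 − 23-Sep-2019 = 168 days = 24.0 weeks, as stated.

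**1. Year-only stop in the starting year.** Start 01-Feb-2019, stop recorded as 2019.
- Imputed stop 01-Jan-2019 precedes the start, so it is reset to 01-Feb-2019.
- Exposure = 01-Feb − 01-Feb + 1 = 1 day.
- Longest true exposure: 31-Dec − 01-Feb + 1 = 334 days (47.7 weeks).
- The result is 1 day for any start date in that year. The cap by death or cut-off is only an upper bound and cannot change it.
- The on-treatment period ends at day 1 + 30 = day 31. Later adverse events leave the on-treatment summaries, although SAP 3.6 still lists them.
- The non-response can be false only if 168 true days fit before year end. In 2019 that needs a start by 17-Jul (31-Dec − 17-Jul + 1 = 168).

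**2. Year-only stop in the following year.** Start 01-Sep-2018, stop recorded as 2019: imputed stop 01-Jan-2019, exposure 123 days (17.6 weeks), against a true maximum of 487.

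**3. Year-only start in 2019.** Imputed index 01-Jan-2019.
- Week 24 window: 01-Jan + 140 days = 21-May, to 01-Jan + 223 days = 12-Aug-2019.
- Example: true start 01-Aug-2019, scan on 15-Jul-2019. True position: 17 days before treatment (week −2.4). Assigned position: 195/7 = week 27.9, inside the window. A scan at true week 24 moves to week 54.3.
- A scan on the true index date falls in the window for any true start from 21-May to 12-Aug.
- Baseline window for the imputed index: 17-Jul-2018 to 01-Jan-2019. If another scan lies there, the pre-treatment scan can serve as the Week 24 scan. If none does, the patient wrongly leaves the efficacy population.

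**4. Only the day of the stop missing.**

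| Start | True stop | True days | Imputed stop | Imputed days | Effect at 168 days |
|---|---|---|---|---|---|
| 10-Mar-2019 | 31-Aug-2019 | 175 | 15-Aug-2019 | 159 | false early discontinuation |
| 01-Mar-2019 | 01-Aug-2019 | 154 | 15-Aug-2019 | 168 | true early discontinuation missed |

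**5. Effect on the response rate.** Clopper-Pearson intervals; the 40% rate is assumed.

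| n | Responders | Rate | 95% CI |
|---|---|---|---|
| 50 | 20 | 40% | 26.4 to 54.8 |
| 50 | 19 (one false non-response) | 38% | 24.7 to 52.8 |
| 50 | 17 (three) | 34% | 21.2 to 48.8 |
| 30 | 12 | 40% | 22.7 to 59.4 |
| 30 | 11 (one) | 36.7% | 19.9 to 56.1 |

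The n = 30 rows are an assumption, shown because the complete-case denominator may be well below 50.

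**The case against.** The strongest reply is that this may never occur. Nothing says alpelisib dates were poorly recorded. Sites need both dates to know which records to abstract (Protocol 6.1). Queries, chronology checks and manual cross-checking against records are planned (Protocol 6.7, 6.10), so the rule may be only a last resort. That stands as a limit on size: the number affected could be zero. It does not make the rule's output correct where it is used, and the checks at data entry are soft warnings.

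Second, the rule sits under a heading on adverse event, medication and safety dates, and no text says the discontinuation criterion is computed from an imputed stop. That is why the non-response is stated conditionally. But SAP 1.3 makes the index date the reference for efficacy as well as safety, and the general default in 4.3.1.2 gives the same dates.

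Third, 01-Jan is not peculiar to treatment dates: Tables 4-1 and 4-3 use it for years after the starting year. This is fair; the contrast is only with the end-date rule in Table 4-2. The asterisk on the imputed end date has no note beside it. If it points to the Table 4-2 definition, that too is an upper cap.

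Three stronger readings are tempting and not supported:
- A reader might infer that the rule admits ineligible patients, since a start recorded as September 2019 becomes 15-Sep and passes the requirement of having "initiated on or before 23-Sep-2019" although 7 of the 30 days are too late. The documents do not say that imputed dates decide inclusion. SAP 3.4 describes screening of programme patients, and SAP 3.2 takes those who meet the criteria.
- A reader might infer that the 15th default can also put a pre-treatment scan into the Week 24 window. Its largest shift is 16 days, against the 140 days at which the window opens.
- A reader might infer that every 1-day exposure is a false non-response. For a patient truly treated for under 168 days, or failing another criterion, non-response is correct.

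**Conclusion.** The point holds as a defect in a stated rule, with limited and unknown reach. A year-only stop in the starting year always gives 1 day of exposure. A year-only start in 2019 can place a pre-treatment or index-day scan in the Week 24 window, or remove the patient from the efficacy population. The 15th default can flip the 24-week criterion near the threshold in either direction. Response status is affected only if the response derivation uses the imputed date and, for a false non-response, only if true treatment reached 168 days and the other criteria were met. Each such patient costs 2 percentage points at n = 50 (1/50), or 3.3 at n = 30 (1/30). The correction is worth making because it is cheap and the endpoint rests on few patients.

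**What to change.** Amend SAP 4.3.1 as follows.

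1. Query sites or programme records for the month and year of first dose, and do not use an imputed start to confirm inclusion criterion 5.
2. For a partial stop date, replace the present default with the earliest of the last day of the recorded month or year, the death date and the cut-off date, and never earlier than the last documented dose or on-treatment record. Table 4-2 cannot be copied whole: its cap includes last treatment date plus 30 days, which is circular here.
3. If the start month stays unknown, list the patient and leave them out of windowed analyses.
4. Where 24-week discontinuation status depends on an imputed date, report the response rate under both the earliest and the latest possible date. The latest date alone would turn short exposures into long ones, and ignoring imputed stops would leave known discontinuers unclassified. The denominator may differ between the two runs, because a patient moved past 24 weeks without a Week 24 scan becomes a missing response.
5. Report how many treatment dates were imputed, separately for start and stop.

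The cost is a few lines of text, a few site queries, one extra run of the primary analysis, and possibly the loss of a patient from windowed analyses.

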4.3.1.1 Imputations and study periods (pre-index, study period)

If "Start" and "End" dates are completely missing with no specification of whether the event is "Ongoing", then the event will be assumed to be happening during the study period.

If "Start" and "End" dates are both missing and "Ongoing" is specified, then the event is assumed to be happening during study period.

In case the "Start" date is completely missing but the "End" date is non- missing or partially missing:

- if end date is in the study period, then the therapy will be assigned only to the study period.
- if end date is before the index date, then the event will be assigned to the pre-index period only.

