## **6 Research methods**

### **6.1 Study design**

This study will be a site-based retrospective non-interventional medical chart review of pediatric and adult male and female patients with PROS. This study will abstract longitudinal information that has been previously recorded in the medical charts of patients with PROS to assess the efficacy and safety of alpelisib for the treatment of the heterogeneous manifestations of PROS.

Patient-level data will be abstracted from medical charts of all eligible patients at all participating sites and will be pooled and assessed. Trained personnel at each site will abstract medical chart data (see [Section 6.4](#) for additional information). Informed consent will be obtained prior to data abstraction, as appropriate, for eligible patients interested in participating in the study.

[figure not shown]
Patients with PROS who have received at least one dose of alpelisib initiated at least 24 weeks before the cut-off date will be included. The index (baseline) date will be defined as the date of alpelisib initiation. The pre-index date period will be defined as the period from up to 24 weeks prior to the index date through one day prior to the index date. The study period will be defined as the period from the index date up to the cut-off date ([Figure 6-1](#)).

The cut-off date (09-Mar-2020) is selected to minimize the impact of the COVID-19 pandemic on the data integrity. Eligible patients who initiated alpelisib on or before 23-Sep-2019 will have relevant assessments expected to occur on or before 09-Mar-2020. At that time of the cut-off, COVID-19 pandemic did not have major consequences on the regular management of the patients in the countries participating in the MAP.

Available information from all clinic visits during the pre-index date period will be abstracted; additionally, available prior PROS medications and PROS related surgical/vascular interventions will be collected since diagnosis.

During the study period, all available data will be collected from index date up to the cut-off date. If a patient has discontinued treatment prior to that date, only data reported up to 30 days after the last date of study treatment will be abstracted and entered into the database.

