#### Endpoints related to objective #5: Description in type of medication and non-drug therapies (e.g., concomitant PROS-related medications, PROS-related surgeries, duration of treatment/response) over time

The endpoints for this objective will describe treatment patterns, including the use of PROS-related medications, including alpelisib and other non-drug treatments, such as surgeries.

The number (%) of patients who have at least one dose adjustment, interruption, or discontinuation, and their reasons, will be presented and summarized. In addition, the duration of treatment will be categorized into time intervals using appropriate units of time; frequency counts and percentages will be presented for the number (%) of patients in each interval.

The number (%) of patients who received any PROS-related medication other than alpelisib during the pre-index date period and the study period will be summarized in addition to the type of PROS-related surgery received and their reasons.

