1.3 Study design and settings

This study will be a site-based retrospective non-interventional medical chart review of pediatric and adult male and female patients with PROS.

Patients with PROS who have received at least one dose of alpelisib initiated at least 24 weeks before the cutoff date (09-Mar-2020) through a Novartis Managed access program (MAP) and satisfy the study inclusion criteria will be included in the study.

Patient-level data will be abstracted from medical charts of all eligible patients at all participating sites and will be pooled and assessed. Trained personnel at each site will abstract medical chart data. Informed consent will be obtained prior to data abstraction, as appropriate, for eligible patients interested in participating in the study where required.

[figure not shown]
The cut-off date of 09-Mar-2020 is selected to minimize the impact of the COVID-19 pandemic on the data integrity. Eligible patients who were initiated alpelisib on or before 23-Sep-2019 are expected to have 24 weeks of relevant assessments on or before 09-Mar-2020. At that time of the cut-off, COVID-19 pandemic did not have major consequences on the regular management of the patients in the countries participating in the MAP.

The **study period** will be defined as the period from the index date up to the cut-off date (09-Mar-2020) (Figure 1-1). During the study period all available data will be collected, if a patient has discontinued treatment prior to the cut-off date only data reported up to 30 days after the last date of study treatment will be abstracted and entered into the database.

The **index date (baseline)** will be defined as the date of alpelisib initiation. This date will be used as reference date for all assessments (safety and efficacy).

The **pre-index date** period will be defined as the period from up to 24 weeks prior to the index date (baseline) through to the day prior to the index date. (Figure 1-1).

Figure 1-1 Study design

Lesion assessments and definition

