3.4 Patient disposition, demographics and other baseline characteristics

Patient disposition

All patients in the MAP will be screened to identify the eligible patients and the number (%) of patients included in the Full study population set will be presented. The number (%) of patients in the Full study population who are still on treatment at the time of the cutoff date, patients who discontinued and the reason for discontinuation will be presented overall and at key time-points.

The number (%) of patients in each analysis set (defined in [Section 3.2](#)) will be summarized overall and at key time-points.

Protocol deviation summaries

The number and percentage of patients in the Full study population with any protocol deviation will be summarized by deviation category. All protocol deviations will be listed.

Demographic and clinical characteristics at index date

All demographic and clinical characteristics information collected at index date and during the pre-index period will be summarized and listed based on the full population set.

Descriptive analyses will be conducted where categorical data (e.g. sex, age groups, ethnicity, PRO subtype, PI3KCA mutation, mosaicism proportion, presence/absence of target and non-target lesions, site of lesions) will be summarized by frequency counts and percentages; the number and percentage of patients with missing data at index date will be provided. Continuous

data (e.g. age, number of lesions) will be summarized by descriptive statistics (N, mean, median, standard deviation, Q1, Q3, minimum and maximum).

Non-medical resource use (e.g., physical therapy, occupational therapy, home care services), frequency of hospitalizations and ER visits, proportion of patients receiving prior PROS-related medication during the pre-index period will be summarized and listed. Prior PROS medications and PROS-related surgical/vascular interventions will be reported since diagnosis, where available.

Separate summaries will be presented for ongoing and historical medical conditions. The summaries will be presented by primary system organ class (SOC) and preferred term (PT). Medical history, comorbidities and current medical conditions will be coded using the Medical Dictionary for Regulatory Activities (MedDRA) terminology. The latest available MedDRA version at the time of the analyses will be used. The MedDRA version used for reporting will be specified in the CSR and as a footnote in the applicable tables/listings.

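### SAP 4.3.1.1 has no 24-week lower limit for records with an unknown start, so prior PROS medication that ended long before alpelisib can count as pre-index use

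*SAP*

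**What the plan says.** SAP 4.3.1.1 decides which period a record belongs to when its start date is completely missing and its end "date is non- missing or partially missing". An end in the study period sends the record to the study period only. For the other case the text is: "if end date is before the index date, then the event will be assigned to the pre-index period only". No earliest date is given.

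The pre-index period itself is bounded. SAP 1.3 defines it as the "period from up to 24 weeks prior to the index date (baseline) through to the day prior to the index date". SAP 4.1 repeats the same limits for adverse event reporting: "from up to 24 weeks prior to the index date through to the day prior to the index date". Protocol 6.1 agrees.

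Medication data reach further back than that. Protocol 6.1 states that "available prior PROS medications and PROS related surgical/vascular interventions will be collected since diagnosis". The planned summaries nevertheless use the short period. SAP 3.4 says that the "proportion of patients receiving prior PROS-related medication during the pre-index period will be summarized and listed". Protocol 6.8.2, objective #5, summarises the patients who "received any PROS-related medication other than alpelisib during the pre-index date period and the study period". SAP 3.4 also reports prior PROS medications since diagnosis, as a separate item.

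**The concern.** A course of treatment that ended five years before alpelisib lies outside a 24-week period on the evidence of its own end date, whatever its start. The rule still places it inside. Because medication history is deliberately taken back to diagnosis, the database can hold such courses. In a retrospective chart review, an old drug with a recorded stop and no recorded start is plausible.

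At stake is the meaning of a planned figure. A proportion labelled as medication use in the 24 weeks before alpelisib could include patients whose only use was much earlier. The study has no control group, and Protocol 6.8.2 plans this summary for the pre-index and study periods side by side, so a reader may well compare the two.

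**Working it through.** There is no stated figure to reproduce. The check is of the rule against the SAP's own definition, and of whether any other rule repairs it.

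**Step 1: the rule against the window.** The pre-index period is 24 × 7 = 168 days. Take 23-Sep-2019 as an example index date, the latest start allowed by inclusion criterion 5. The window then runs from 08-Apr-2019 to 22-Sep-2019. For records with a completely missing start:

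| End date | Weeks before index | SAP 4.3.1.1 as written | SAP 24-week definition |
|---|---|---|---|
| 01-Aug-2019 | 7.6 | pre-index | pre-index |
| 08-Apr-2019 | 24.0 | pre-index | pre-index |
| 07-Apr-2019 | 24.1 | pre-index | before the window |
| 31-Dec-2018 | 38.0 | pre-index | before the window |
| 30-Jun-2014 | 273.0 | pre-index | before the window |

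The last three rows are assigned to a period that their end dates exclude.

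**Step 2: does another rule remove such records?**
- Table 4-1 leaves a completely missing start unimputed, so 4.3.1.1 alone decides.
- Table 4-3 does hold some imputed dates at the pre-index date. It covers other record types (laboratory data, surgery, disease history and similar), and only partly missing dates.
- Section 4.3.1 defers further detail on the pre-index period to the programming specifications but states no limit.
- The since-diagnosis report in SAP 3.4 is an additional output. It does not restrict what enters the 24-week one.

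**Step 3: size per patient.** Let N be the number of patients, u the number with true use in the 24 weeks, and k the number counted only because of an old record. The reported proportion is (u + k)/N, against a true u/N. The difference, k/N, cannot be negative. With N = 50 (the figure used in Protocol 6.6), each such patient adds 1/50 = 2 percentage points.

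Illustration, with u = 20 assumed (20/50 = 40%):

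| k (assumed) | Reported proportion |
|---|---|
| 0 | 40% |
| 1 | 21/50 = 42% |
| 3 | 23/50 = 46% |
| 5 | 25/50 = 50% |
| 10 | 30/50 = 60% |

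The documents give neither u nor k, and k may be 0.

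**Step 4: partial end dates.** Table 4-2 moves a year-only end to 31 December (or the end of the study period, if earlier). Assume an index date of 15-Mar-2019 and an end known only as 2018. The imputed end is 31-Dec-2018, which is 31 + 28 + 15 = 74 days (10.6 weeks) before index and so inside the window. The course may have stopped at any time in 2018. A lower limit alone therefore leaves some records whose class depends on the imputation.

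**The case against.** The strongest defence is that the final phrase of the bullet only means that the record does not belong to the study period. On that reading, SAP 1.3 and 4.1 still govern which records fall within 24 weeks, and the programming specifications supply the detail. This is a possible intention, but the text assigns the record to a period with a defined length, and a programmer following it would produce the miscount. The specifications are not part of these documents.

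Other objections stand and limit the point:
- **Scope.** A reader might infer that symptoms, complications and resource use before alpelisib are inflated in the same way. The documents do not support this to the same degree. Under Protocol 6.1, pre-index information comes from clinic visits within the 24 weeks; only prior PROS medications and surgical or vascular interventions go back to diagnosis, and surgery falls under Table 4-3. Historical medical conditions have their own summary in SAP 3.4, and nothing says that they feed the pre-index symptom table.
- **Direction overall.** A reader might infer a bias in favour of alpelisib. That is not shown. Under 4.3.1.1, records with both dates missing go to the study period, and an unknown start with an on-study end goes to the study period only. Table 4-2 extends completely missing ends to the end of the study period. Table 4-1 sets many partial starts in the index month or year to the index date. These rules raise on-study counts or lower pre-index counts.
- **Role of the figure.** Pre-index summaries are not the study's only baseline. Symptom changes, including pain, are assessed from the index date. All these analyses are descriptive.
- **Frequency.** Day, month and year of the start must all be missing. A start with only the year known follows Table 4-1 instead.

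**Conclusion.** The contradiction is real: the bullet has no lower limit, the period it assigns to is at most 24 weeks long, and nothing else in the SAP or protocol repairs this. It is well supported for prior PROS-related medications, through the pre-index proportions in SAP 3.4 and Protocol 6.8.2.

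For these records the error has one direction: the pre-index proportion rises or stays the same, by 2 points per affected patient at N = 50. That assumes the patient has no other qualifying pre-index use. The total size cannot be derived from the documents and may be zero. Any statement about what share of such records is misassigned would need an assumed spread of end dates and time since diagnosis, neither of which is given. The net effect of all the date rules on a before/after comparison is undetermined.

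The primary response endpoint is unaffected. This is a small defect in a descriptive secondary summary, worth correcting because the correction is almost free.

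**What to change.** Replace the second bullet of SAP 4.3.1.1 with wording such as:

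> If the end date, after Table 4-2 imputation, lies before index and no earlier than index minus 24 weeks, assign the record to the pre-index period alone. If it lies earlier, assign it to neither period and report it only under history since diagnosis.

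Report the number of missing-start records in each class, and flag those whose class depends on an imputed end date. Applying the limit after Table 4-2 keeps it consistent with the existing end-date rules, and the flag shows how much rests on them.

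The cost is one added date comparison in programming, a short count table, and a pre-index medication proportion that may come out slightly lower. The change does not address the neighbouring rules that push the other way, so it should not be presented as making the before/after comparison unbiased.
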